7.4.2.2 Gastrointestinal Events

Carfilzomib treatment can cause nausea, vomiting, diarrhea, or constipation sometimes requiring the use of antiemetics or antidiarrheals. Fluid and electrolyte replacement should be administered to prevent dehydration. Routine premedication with antinausea or antidiarrheal agents is not required. Carfilzomib should be held if these events persist after symptomatic treatment, are Grade 3 or greater and determined by the Investigator to be related to the Carfilzomib.

7.4.2.3 Hematologic Toxicity

Typically, there is no dosages adjustment related to hematological toxicity with the R-ICE regimen as described in this study. C-R-ICE will be planned to be given on a q 21 - 28 day cycle. C-R-ICE will be postponed until neutrophil counts reach $\geq 1 \times 10^9/L$ and platelet counts $\geq 50 \times 10^9/L$.

7.4.2.4 Tumor Lysis Syndrome

Suspected or documented TLS or multiorgan failures have been observed in some patients treated with carfilzomib in the Phase II studies prior to the institution of TLS prophylaxis guidelines. Patients with high tumor burden or compromised renal function may be at elevated risk, and should be closely monitored, and uric acid levels normalized prior to initiation of treatment, if appropriate. Adequate oral and IV hydration and premedication with dexamethasone 4 mg PO or IV are required prior to initiation of therapy with carfilzomib, at least in Cycle 1. If TLS occurs, carfilzomib should be held until the event has resolved. Prophylaxis should be reinstated and the patient should be monitored carefully. Additional safety measures are described in detail in the protocols.

7.4.2.5 Infusion Reactions and Adverse Events Experienced within a Day of Dosing

True infusion reactions have been reported but are rare. Should an infusion reaction occur, treatment with glucocorticoids, IV fluids, vasopressors, oxygen, bronchodilators, and acetaminophen should be available for immediate use and instituted as medically indicated. Adverse events have been observed with carfilzomib that include fever, chills, dyspnea, and/or rigors occurring in the evening following the first day of infusion during the first cycle of therapy, which may be the clinical sequelae of rapid tumor lysis or cytokine release; this has been associated with an increase of creatinine on the second day. Cytokine release has been documented in animals treated with carfilzomib. Management guidelines were instituted which included premedication with dexamethasone (4 mg PO on Days 1, 2, 8, and 9 or equivalent) and starting patients at a 20 mg/m^2 dose for a minimum of 2 days before dose escalation. These management guidelines and stepped-up dosing were generally effective at alleviating AEs

experienced within the first day of dosing in further studies. If fevers or chills persist after the first cycle, continued premedication with dexamethasone is recommended.

7.4.2.6 Renal Impairment

Grade 1 and Grade 2 reversible increases in creatinine were reported. Renal failure has been reported less frequently. It is not known if there is a clear association between renal failure and carfilzomib. Many cases of renal failure were confounded by documented or suspected TLS, sepsis/infections, light-chain disease, and disease progression. Renal function should be monitored prior to each dose in Cycle 1 and Cycle 2 and in patients experiencing increases in creatinine \geq Grade 2. Carfilzomib has been characterized in patients with CrCL < 15 mL/min or creatinine ≥ 2.5 mg/dL. Studies in patients with very severe renal dysfunction and those receiving hemodialysis demonstrated there were no major differences in the observed safety findings among patients with renal dysfunction compared to those with normal renal function.

7.4.2.7 Hepatic Impairment

Three cases of hepatic failure (including 2 cases that were precursors to the patients' death due to end-stage progression of their MM) and 1 case of veno-occlusive has been reported with the use of carfilzomib (refer to Carfilzomib Investigator's Brochure). Non-serious and serious (Grade 1 - 3) transaminitis have been reported infrequently. Carfilzomib dosage should be held in patients who experience a liver abnormality \geq Grade 3. If the event resolves within 2 weeks, carfilzomib may be restarted at a reduced dose and monitored carefully. The use of carfilzomib has not been characterized in patients with hepatic impairment.

7.4.2.8 Other Conditions Delaying Treatment

If posterior reversible encephalopathy syndrome (PRES) is suspected, carfilzomib should be held. The patient should then be evaluated with MRI and for onset of visual or neurological symptoms suggestive of PRES. If PRES is confirmed, carfilzomib should be permanently discontinued. If a diagnosis of PRES is excluded, carfilzomib may be restarted per the discretion of the PI.

Carfilzomib should be held if thrombotic microangiopathy (TMA) is suspected and patient should be managed per institutional standard of care, which may include plasma exchange, if appropriate. If TMA is confirmed, carfilzomib should be permanently discontinued. If TMA is ruled out, then carfilzomib may be restarted per the discretion of the PI.

If the patient experiences a hypertensive crisis, carfilzomib should be held until the resolution of the event to the patient's baseline. Carfilzomib may then be restarted at 1 dose decrement.

7.4.2.9 Mechanisms of Action

Carfilzomib is a tetrapeptide epoxyketone proteasome inhibitor that binds selectively and irreversibly to the N-terminal threonine containing active sites of the 20S proteasome and displays little to no activity against other classes of proteases. In vitro, carfilzomib has been shown to have antiproliferative and proapoptotic activities across a range of solid and hematologic tumor cells, including cells that are resistant to bortezomib. Carfilzomib does not

induce neurite degeneration in differentiated neuronal cell lines sensitive to an equimolar concentration of bortezomib. *In vivo*, carfilzomib results in rapid and sustained inhibition of proteasome activity in blood and tissues and delays tumor growth in MM, hematologic, and solid tumor animal models, including bortezomib-insensitive human tumor xenograft models.

8 GENERAL CONCOMITANT MEDICATION AND SUPPORTIVE CARE

8.1 Safety Considerations

Based upon the experience in the Phase I and Phase II clinical studies with carfilzomib, the following observations are noted:

- A “first dose effect” has been seen, which is notable for fever, chills, rigors, and/or dyspnea occurring during the evening following the first day of infusion and an increase in creatinine on Day 2, which may be the clinical sequelae of rapid tumor lysis and/or cytokine release.
- Should a “first dose” effect occur at any point during Cycle 1 or Cycle 2, treatment with high dose glucocorticoids (e.g., methylprednisolone 50 mg - 100 mg) is recommended. In addition, intravenous fluids, vasopressors, oxygen, bronchodilators, and acetaminophen should be available for immediate use and instituted, as medically indicated.
- Dexamethasone 4 mg PO/IV will be administered prior to all carfilzomib doses.
- Acyclovir or similar should be given to all subjects with a history of herpes simplex or zoster, per institutional prophylaxis guidelines, unless contraindicated.
- CrCL changes are mostly transient, reversible, and non-cumulative. All subjects should be well hydrated. Clinically significant electrolyte abnormalities should be corrected prior to dosing with carfilzomib. Renal function must be monitored closely during treatment with carfilzomib. Serum chemistry values, including creatinine, must be obtained (within 24 hours) and reviewed prior to each dose of carfilzomib. Carfilzomib must be held for subjects with a CrCL < 30 mL/min at any time during study participation.
- Subjects with active or suspected infection of any kind that required systemic treatment should not be dosed with carfilzomib until the infection has resolved and if being treated with anti-infective, the course of antibiotics has been completed.
- Thrombocytopenia has been transient and typically resolves during the week between treatments. For platelet counts \leq 50,000/mm³, carfilzomib dosing must be held before proceeding to the next cycle of C-R-ICE.
- Subjects should have anemia corrected in accordance with the Institutional guidelines.
- Carfilzomib treatment can cause nausea, vomiting, diarrhea, or constipation sometimes requiring the use of antiemetics or antidiarrheals. Fluid and electrolyte replacement should be administered to prevent dehydration.

8.2 Guidelines for Monitoring, Prophylaxis, and Treatment of Tumor Lysis Syndrome

- Tumor Lysis Syndrome (TLS), which may be associated with multiorgan failure, has been observed in treatment Cycle 1 and Cycle 2 in some patients with MM who have been treated with carfilzomib.

The following safety measures are mandatory for all subjects:

- In addition, subjects with high tumor burden or rapidly progressing DLBCL or compromised renal function ($\text{CrCL} < 50 \text{ mL/min}$) should be considered to be at particularly high risk.

Hydration and Fluid Monitoring

- Oral hydration: All subjects must be well hydrated (i.e., volume replete). Begin oral hydration equal to approximately 30 mL/kg/day (approximately 6 – 8 cups of liquid per day), starting 48 hours prior to the planned first dose of carfilzomib. Compliance must be reviewed with the subject and documented by the site personnel prior to initiating treatment with carfilzomib; treatment is to be delayed or withheld if oral hydration is not deemed to be satisfactory.
- Intravenous Fluids: 250 - 500 mL of IV normal saline (or other appropriate IV fluid formulation) must be given before and after each carfilzomib dose during Cycle 1. If lactate dehydrogenase (LDH) or uric acid is elevated at Cycle 2, Day 1, then the recommended IV hydration should be repeated for Cycle 2. The goal of the hydration program is to maintain robust urine output, (e.g., $\geq 2 \text{ L/day}$). Subjects should be monitored periodically during this period for evidence of fluid overload.
- In subjects considered to be still at risk for TLS at completion of Cycle 1, hydration should be continued in Cycle 2, if clinically indicated. Patients in whom this program of oral and IV fluid hydration is contraindicated, e.g., due to pre-existing pulmonary, cardiac, or renal impairment, will not be eligible to participate in the clinical trial.

Laboratory Monitoring

- Appropriate chemistries, including creatinine, and complete blood counts (CBC) with platelet count should be obtained and reviewed prior to carfilzomib dosing on day 1 of each cycle. Results of laboratory studies must be reviewed and deemed acceptable prior to administering the carfilzomib dose. Subjects with laboratory abnormalities consistent with lysis of tumor cells (e.g., serum creatinine $\geq 50\%$ increase, LDH ≥ 2 -fold increase, uric acid $\geq 50\%$ increase, phosphate $\geq 50\%$ increase from baseline, potassium $\geq 30\%$ increase, calcium $\geq 20\%$ decrease) prior to dosing should not receive the scheduled dose. Subjects with such abnormalities should be re-evaluated again within the next 24 hours (or sooner, if clinically indicated) and then periodically as clinically indicated.

Clinical Monitoring

- Inform subjects of signs and symptoms that may be indicative of TLS, such as fevers, chills/rigors, dyspnea, nausea, vomiting, muscle tetany, weakness, or cramping, seizures, and decreased urine output. Advise subjects to report such symptoms immediately and seek medical attention.

Management of Tumor Lysis Syndrome

- If TLS occurs, cardiac rhythm, fluid, and serial laboratory monitoring should be instituted. Correct electrolyte abnormalities, monitor renal function and fluid balance, and administer therapeutic and supportive care, including dialysis, as clinically indicated.

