6.1.2. Drug Preparation and Administration

Carfilzomib for injection is supplied as a lyophilized parenteral product in single-use vials. The lyophilized product is reconstituted with water for injection to a final carfilzomib concentration of 2 mg/mL prior to administration. The dose will be calculated using the subject's actual BSA at baseline. Subjects with a BSA > 2.2 m² will receive a dose based upon a 2.2 m² BSA.

IV hydration will be given immediately prior to carfilzomib during Cycle 1. This will consist of 250 mL to 500 mL normal saline or other appropriate IV fluid. If lactate dehydrogenase (LDH) or uric acid is elevated (and/or in subjects considered still at risk for TLS) at Cycle 2 Day 1, then the recommended IV hydration should be given additionally before each dose in Cycle 2. The goal of the hydration program is to maintain robust urine output (e.g., \geq 2 L/day). Subjects should be monitored periodically during this period for evidence of fluid overload.

If the subject has a dedicated line for carfilzomib administration, the line must be flushed with a minimum of 20 mL of normal saline prior to and after drug administration.

Carfilzomib will be given as an IV infusion over approximately 10 minutes. For doses > 27 mg/m², carfilzomib should be infused over 30 minutes. The dose will be administered at a facility capable of managing hypersensitivity reactions. Subjects will remain at the clinic under observation for at least 1 hour following each dose of carfilzomib in Cycle 1 and following the dose on Cycle 2 Day 1. During these observation times, post dose IV hydration (between 250 mL and 500 mL normal saline or other appropriate IV fluid formulation) will be given. Subjects should be monitored periodically during this period for evidence of fluid overload.

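### Sections 6.1.2 and 8.2 give different IV hydration instructions for Cycle 2 and need to be reconciled; the cup equivalent of the oral target in 8.2 needs a minor clarification

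*Combined protocol and SAP*

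**What the plan says.** Two sections of the protocol set out the fluid programme that accompanies carfilzomib.

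**Section 8.2** introduces its measures with "The following safety measures are mandatory for all subjects".
- Oral: "Begin oral hydration equal to approximately 30 mL/kg/day", with a parenthetical equivalent of about 6 to 8 cups a day, starting 48 hours before the first dose. Site staff must review and document compliance, and "treatment is to be delayed or withheld if oral hydration is not deemed to be satisfactory".
- IV, Cycle 1: 250-500 mL "must be given before and after each carfilzomib dose during Cycle 1".
- IV, Cycle 2: if LDH or uric acid is raised on Day 1, "then the recommended IV hydration should be repeated for Cycle 2". A separate bullet continues hydration for patients still at TLS risk after Cycle 1, subject to clinical indication.

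**Section 6.1.2** covers the same IV fluid, with the same 250-500 mL per administration.
- Before the dose: given in Cycle 1. If LDH or uric acid is raised on Cycle 2 Day 1, and/or the patient is still considered at TLS risk, "then the recommended IV hydration should be given additionally before each dose in Cycle 2".
- After the dose: patients are observed "for at least 1 hour following each dose of carfilzomib in Cycle 1 and following the dose on Cycle 2 Day 1", and post-dose IV fluid is given during those observation periods. No laboratory trigger is attached.

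Separately, Section 8.3.1 requires all patients to receive the hydration usual for R-ICE under institutional guidelines.

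**The concern.** Both sections govern the same fluid, in the same patients, in the same cycle, but a site that works from one will not do what the other describes. Section 8.2 itself records that TLS has been seen in Cycle 2 as well as Cycle 1 in myeloma patients given carfilzomib. Section 1.4.4 reports Grade 3/4 renal impairment falling from 15% to 2.2% between two parts of an earlier carfilzomib study, and attributes this most likely to hydration together with very low dose dexamethasone.

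Safety at the selected dose is a Phase Ib primary objective (Section 3.2), and network sites take part in Phase Ib only (Section 4.2). If sites follow different sections, Cycle 2 renal and TLS findings would reflect different supportive care as well as the study treatment.

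The oral text raises a smaller question. A weight-based volume and a fixed number of cups cannot agree across adults of all sizes, and the text does not say which one the documented compliance review should use.

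**Working it through.** **1. IV fluid in Cycle 2, side by side**

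| Situation at Cycle 2 Day 1 | Section 6.1.2 | Section 8.2 |
|---|---|---|
| LDH or uric acid raised | Before each dose; after the Day 1 dose only | Cycle 1 scheme repeated: before and after each dose, on the natural reading |
| Neither raised, not at TLS risk | After the Day 1 dose | None specified |
| Neither raised, still at TLS risk | Before each dose (should be given); after the Day 1 dose | Continued only where clinically indicated |

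The sections agree on Cycle 1 and on pre-dose fluid in Cycle 2 when LDH or uric acid is raised.

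**2. Size for a triggered patient**

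Inputs: v = 250-500 mL per administration (both sections) and d = carfilzomib doses in Cycle 2. The treatment schema (Figure 6) is not reproduced in the text available, so d is an assumption. The range used is 2 to 4. Section 14.2 describes infusions on Days 1 and 2 of Cycle 1; Table 3, footnote 9, schedules chemistry on Days 1, 2, 8 and 9.

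- Section 6.1.2: d pre-dose plus 1 post-dose, so (d + 1) × v.
- Section 8.2, repeating Cycle 1: 2d × v.
- Relative shortfall under 6.1.2: 1 − (d + 1)/(2d), which does not depend on v.

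| d | Section 6.1.2 | Section 8.2 | Shortfall |
|---|---|---|---|
| 2 | 3 × 250-500 = 750-1,500 mL | 4 × 250-500 = 1,000-2,000 mL | 1 − 3/4 = 25% |
| 4 | 5 × 250-500 = 1,250-2,500 mL | 8 × 250-500 = 2,000-4,000 mL | 1 − 5/8 = 37.5% |

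For a patient who is neither triggered nor at TLS risk, 6.1.2 specifies 250-500 mL once and 8.2 specifies nothing. These volumes exclude the institutional R-ICE hydration of Section 8.3.1.

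**3. Oral equivalence**

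The plan's 6 to 8 cups cannot be reproduced, because the documents give neither a cup volume nor a reference body weight. The weight at which the two expressions agree is cups × mL per cup ÷ 30. Cup volumes are assumptions.

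- 237 mL: 6 × 237/30 = 47.4 kg to 8 × 237/30 = 63.2 kg.
- 250 mL: 6 × 250/30 = 50.0 kg to 8 × 250/30 = 66.7 kg.
- 284 mL: 6 × 284/30 = 56.8 kg to 8 × 284/30 = 75.7 kg.

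Allowing for approximation by going up to 8.5 of the largest cups gives 8.5 × 284/30 = 80.5 kg. At 100 kg the weight-based figure is 30 × 100 = 3,000 mL a day, against 8 × 237 = 1,896 mL to 8 × 284 = 2,272 mL from eight cups.

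**The case against.** The best reply is that the sections can be followed together. Section 8.2 does not forbid fluid it fails to mention, and giving fluid before and after every Cycle 2 dose to a triggered patient satisfies both texts. On that view the difference is one of detail. This does not dispose of the point: a site working from 6.1.2 alone would omit post-dose fluid that 8.2, on its natural reading, calls for.

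Several qualifications do stand.
- Reading the repeat in 8.2 as before and after each dose is an inference, though the natural one.
- The Cycle 2 wording in both sections is advisory (should, recommended), even though the 8.2 heading speaks of mandatory measures.
- The volumes are not what patients would actually receive, because R-ICE hydration is added. A reader might infer that an untriggered patient gets no IV fluid under 8.2; Section 8.3.1 does not support that.
- The earlier fall in renal events is credited to hydration and dexamethasone jointly, and Section 8.1 requires dexamethasone before every carfilzomib dose.
- Phase Ib has only 9 patients, which limits any between-site effect.

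A reader might also infer that the two oral figures are competing rules leading to different dosing decisions. The documents do not support that. There is one weight-based target with an approximate lay equivalent, no cup size is defined, and the condition for dosing is a judgement that hydration is satisfactory, with no volume cutoff.

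**Conclusion.** The IV inconsistency is real. For Cycle 2, Sections 6.1.2 and 8.2 differ on post-dose fluid for triggered patients, on whether untriggered patients receive fluid after the Day 1 dose, and on how firmly fluid is called for in patients still at TLS risk with normal LDH and uric acid. For a triggered patient the specified IV volume is 25% to 37.5% lower under 6.1.2. This rests on the natural reading of 8.2, an assumed two to four doses per cycle, and the same volume at each administration.

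It would be wrong to infer an effect on dose finding or on the efficacy test. DLTs are counted in Cycle 1 only (Section 7.4.1), where the two sections agree on IV fluid, and Section 4.1 already fixes the Phase Ib dose level. Sample size, alpha and power do not depend on hydration. What is at stake is consistent TLS and renal protection and a Phase Ib safety assessment that means the same thing at every site.

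The oral wording is a minor ambiguity: the cup equivalent fits about 47-63 kg with a 237 mL cup and about 57-76 kg with a 284 mL cup, and understates the weight-based figure for heavier patients.

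**What to change.** Reconcile Sections 6.1.2 and 8.2 to a single statement for Cycle 2 covering the trigger (including patients still at TLS risk with normal laboratory values), the days, and pre-dose versus post-dose fluid. Place it in one section and refer to it from the other. In 8.2, reconcile the two oral expressions and say which is the standard for the documented compliance review. The content of both is for the clinical team; this review takes no view on which hydration rule is right. The cost is protocol wording in two sections, with no change to sample size or analysis.

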8.3 Concomitant Medications

Concomitant medication is defined as any prescription or over-the-counter preparation including vitamins and supplements. Concomitant medications will not be collected at this time.

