3.3. Secondary Objectives

- To determine the feasibility of successful mobilization of autologous stem cells (i.e., minimum of 2×10^6 CD34+ cells/kg should be collected) to be used for ASCT (if applicable).
- To determine toxicities associated with C-R-ICE salvage therapy.
- To determine the TTP, PFS, and OS followed by ASCT (if applicable); Disease-free survival in CR patients.
- To determine the pharmacokinetics/pharmacodynamics relationship between carfilzomib's degree of proteasome inhibition and response rate along with the time course of thrombocytopenia.
- To study differences in clinical outcomes between GCB and non-GCB relapsed/refractory DLBCL following therapy with carfilzomib and R-ICE.

[figure not shown]
Correlative translational research studies to include: phenotypic/genotypic analysis and functional activity (i.e., ADCC and CMC) of patient's peripheral blood mononuclear "effector" cells (PBMC), as well as ex vivo analysis of sensitivity of primary tumor cells to various combinations of carfilzomib versus Bortezomib +/- rituximab; enzymatic assay for chymotrypsin-like activity to determine the degree of proteasome inhibition in primary DLBCL patient samples and patient PBMC specimens; explorative analysis to identify potential factors predictive of response to therapy will be performed (as part of an NIH-supported R01 grant: R01 CA136907-0A1; PI: [name]).

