8.3.1 Required Concomitant Medications

- Female subjects of child-bearing potential must agree to use dual methods of contraception for the duration of the study and for at least 30 days after the last dose of carfilzomib. Male subjects must agree to use a barrier method of contraception for the duration of the study if sexually active with a female of child-bearing potential. Male subjects must also refrain from donating sperm for at least 90 days after the last dose of carfilzomib.
- Subjects should receive antibiotic prophylaxis with ciprofloxacin or other fluoroquinolone (or trimethoprim/sulfamethoxazole if fluoroquinolones are contraindicated). In addition, subjects should receive acyclovir or similar (famciclovir, valacyclovir) anti-varicella (anti-herpes) agent prophylaxis.
- Subjects should receive adequate granulocyte colony stimulating factor support on Day 8 of treatment.
- All subjects must receive prophylaxis with hydration as typically used for R-ICE per institutional guidelines.
- Subjects may be pretreated for nausea and vomiting with appropriate anti-emetics.
- Patients may receive transfusion support as per institutional guidelines.

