14.2 PK/PD Model Development

A pharmacologically-driven PK/PD model will be developed to elucidate the temporal relationship between carfilzomib concentrations and the time course of proteasome inhibition, along with temporal relationships with thrombocytopenia and neutropenia. This model will allow assessment of the dose and schedule at which carfilzomib facilitates maximal proteasome inhibition and thus lead to an increase response rate, while modulating the degree of severe toxicities. In addition, the effect of concomitant administration of rituximab, ifosfamide, carboplatin, and etoposide will be incorporated into the model to assess their potential effects on efficacy and/or toxicity.

First, a variety of compartmental population PK structural models will be evaluated to characterize the plasma concentration versus time profile following administration of carfilzomib using a nonlinear mixed effects modeling approach NONMEM®. The physiologic pharmacokinetic models explored will be described by the estimation of mean structural model

parameters (e.g. plasma volumes of distribution and clearances), the magnitude of inter-animal variability (IIV) in these parameters and the magnitude of residual variability (RV). For each model, the fit will be assessed by examination of several diagnostics. For comparisons of hierarchical models, the change in the minimum value of the objective function (MVOF), a statistic that is proportional to minus twice the log likelihood of the data, will be examined.

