Using a sequential approach, a population PK/PD structural model will be developed for carfilzomib based on degree of proteasome inhibition in relation to efficacy and toxicity endpoints in the proposed study using NONMEM. This PK/PD model will describe the potential relationship between carfilzomib exposure in relation to proteasome inhibition to the time course of thrombocytopenia and neutropenia as indicators of pharmacodynamic response. The relationship between carfilzomib concentrations and these pharmacodynamic endpoints will be initially explored graphically and various structural models will be applied to the data and evaluated. Similar to the PK model development, criteria such as the precision of parameter estimates, magnitude of residual variability, and goodness-of-fit will be utilized for PK/PD model selection. The PK/PD model could be expanded to include attributes that are indicators of pharmacodynamic response from the concomitant medications of rituximab, ifosfamide, cisplatin, and etoposide which will modulate the overall response rate.

Assay for Proteasome Inhibition. This measures (but does not distinguish from) the activity of beta5 (constitutive proteasome) and LMP7 (immunoproteasome). Analysis of biomarkers that predict for response following treatment with proteasome inhibitors will also be performed on PBMC and whole blood plasma samples ((1) 10 ml green top tube with each blood draw) taken at time points below in Cycle 1 only: Day 1 of Cycle 1, pre-dose and 1 hr post end of infusion; Day 2 of Cycle 1, pre-dose and 1 hr post end of infusion and Day 3, Cycle 1, prior to rituximab administration..

Samples will be sent to Roswell Park Department of Medicine Lymphoma/Myeloma Laboratory for processing. Tube station #621 in Roswell Park Cancer Cell Center.

For additional information regarding the handling of samples please contact [name] at [contact] or [contact].

Furthermore, the final PK/PD model will be used to conduct a clinical trial simulation to predict pharmacokinetic outcomes of various dosing regimens (94, 95) to guide dosing and scheduling of C-R-ICE in relation to safety and efficacy endpoints. The simulation results will allow prediction of the exposure-response relationships for different doses and schedules of carfilzomib to achieve the desired responses.

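### The PK/PD model is fitted to platelet and neutrophil time courses, but the plan does not record platelet transfusions or G-CSF and has no rule for counts taken after them

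*Combined protocol and SAP*

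**What the plan says.** - **Model.** Section 14.2 sets out a population PK/PD model of carfilzomib concentration and proteasome inhibition, "along with temporal relationships with thrombocytopenia and neutropenia". It takes the "time course of thrombocytopenia and neutropenia as indicators of pharmacodynamic response". The final model is to be used in simulation to guide dosing and scheduling.
- **Objective.** Section 3.3 covers the relation of proteasome inhibition to response, "along with the time course of thrombocytopenia". Neutropenia is not named there; it enters only in 14.2 (repeated in the synopsis).
- **Counts.** Table 3, footnote 8, calls for blood counts three times a week between cycles until recovery.
- **Support.** Section 8.3.1 states: "Subjects should receive adequate granulocyte colony stimulating factor support on Day 8 of treatment", and "Patients may receive transfusion support as per institutional guidelines". Section 7.4.2 also mentions transfusion for thrombocytopenia. Section 6.7 lists pegfilgrastim, filgrastim and biosimilars without fixing one.
- **Recording.** Section 8.3 gives the definition "Concomitant medication is defined as any prescription or over-the-counter preparation including vitamins and supplements", followed by "Concomitant medications will not be collected at this time". Table 3, its footnotes and Section 16.1 have no item for transfusions or for G-CSF product, dose or dates.
- **Model inputs.** The only co-treatments that 14.2 names are the other drugs of the regimen.

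**The concern.** The counts that serve as the toxicity response are taken in the same weeks in which platelets may be transfused and G-CSF is given. If the model is fitted without knowing when that happened, a rise due to transfusion is read as the patient's own recovery. For platelets the error is not random. The patients with the lowest counts are the ones likely to be transfused, and if toxicity rises with exposure they are mainly those with the highest exposure. The fitted relation would then be too shallow. A simulation built on it could make higher exposure look better tolerated than it was.

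**Working it through.** The plan gives no figure on this point to reproduce. The check has two parts.

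**1. Do the premises hold together?**

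- The modelled response includes platelet and neutrophil time courses (14.2).
- The counts span the support period (Table 3, footnote 8).
- Support is expected in that period (7.4.2 and 8.3.1). Section 13.5.1 describes blood products and growth factor as part of standard care.
- G-CSF falls within the 8.3 definition and so is not collected. Blood products are not clearly within the definition, but no other section provides for recording them.
- Section 14.2 has no rule for counts taken after either intervention.
- PK/PD samples come from Phase I only (9.4; Table 3, footnote 24), so at most 21 patients are involved.

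**2. Which way, and how far, could the platelet relation move?**

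The documents give no trigger, transfusion rate or platelet increment, so every input below is an assumption. A transit-compartment platelet model was simulated for 21 patients over 28 days. It had about three counts a week, a carfilzomib effect on Days 1, 2, 8 and 9, and a chemotherapy effect. A count below the trigger led to a transfusion. The triggering count was kept at its pre-transfusion value, and transfused platelets had a half-life of 3 days. The fit ignored the transfusions. Twelve replicates were run per setting, with a Monte Carlo standard error of roughly 4 to 9 percentage points of the true slope.

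Change = (slope with transfusions ignored ÷ slope in the same patients with no transfusion) − 1. Counts are in ×10⁹/L. Brackets show the change and the share of patients transfused.

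| Median nadir, no transfusion | Slope, no transfusion | Trigger 10, rise 30 | Trigger 20, rise 20 | Trigger 20, rise 40 |
|---|---|---|---|---|
| 36 | 0.129 | 0.126 (−2%; <1%) | 0.118 (−9%; 6%) | 0.113 (−12%; 6%) |
| 26 | 0.160 | 0.149 (−7%; 2%) | 0.123 (−23%; 26%) | 0.104 (−35%; 26%) |
| 20 | 0.160 | 0.137 (−14%; 6%) | 0.105 (−34%; 50%) | 0.081 (−49%; 50%) |
| 12.6 | 0.162 | 0.091 (−44%; 29%) | 0.091 (−44%; 85%) | 0.071 (−56%; 85%) |
| 9.9 | 0.264 | 0.114 (−57%; 51%) | 0.111 (−58%; 90%) | 0.090 (−66%; 90%) |

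Two harsher settings, with a median untransfused nadir below 1 and every patient transfused, lost 85% or more. They are left out because the nadirs are too extreme to be a useful illustration.

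A cruder simulation regressed log nadir on dose level: 21 patients, 6 levels, an assumed median nadir of 45 falling about 18% per level, and a rise of 20. It gave losses of:

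- trigger 10: 1 − 0.195/0.196 = 0.5%
- trigger 20: 1 − 0.174/0.203 = 14%
- trigger 30: 1 − 0.138/0.202 = 32%

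Both approaches agree on direction. The spread in size comes from the assumptions. G-CSF was not simulated.

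**The case against.** Several points on the other side are sound and limit the finding.

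- **Section 8.3 does not expressly rule out recording transfusions.** Its definition covers prescription and over-the-counter preparations. A reader might infer that the plan forbids recording transfusions; it does not. For platelets the gap is silence. Table 3 lists tests and observations, and the database design under 16.1 is not shown, so an absent row is weak evidence alone. Still, nothing in the plan calls for the data or says how the model would use them.
- **The records probably exist.** Section 4.2 limits network sites to Phase Ib, so Phase I patients were treated at one institution. Section 7.3 requires neutrophil recovery without G-CSF before retreatment, so treating staff need to know its timing. This makes the fix feasible. It does not put the data into the model.
- **G-CSF on a fixed day is near-uniform.** Its nominal day can be modelled, and alone it need not distort the exposure slope. The remaining risk lies in product, number of doses and duration, which are not fixed and could affect the recovery parameters.
- **Proteasome inhibition is untouched.** It is measured directly and is also a pharmacodynamic endpoint.
- **The triggering low count stays in the data.** This is true, and the transit-compartment simulation kept it. The slope still shrank because later counts were raised.
- **The percentages do not estimate bias in the planned analysis.** This is correct. The plan is a NONMEM mixed-effects model, and neither simulation reproduces it.
- **The trial's own dose decision does not rest on this model.** A reader might infer that the choice of dose is compromised. The documents do not support that: escalation follows Table 2, and Section 4.1 already sets the Phase Ib dose from the Phase I results.

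**Conclusion.** The gap is real and worth closing before the model is fitted. As written, the plan lets unrecorded platelet transfusions enter the platelet time course, which could bias the exposure-toxicity relation toward understating toxicity. The direction rests on one assumption: that transfusion is given in response to low counts. The size could be negligible if transfusion was rare and substantial if about a quarter or more of the patients were transfused. The planned dataset could not distinguish these cases.

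A reader might conclude that the model will be biased, or biased by a known percentage, or that both cytopenias are a stated secondary objective. The documents support none of these: transfusion frequency is not given, the simulated figures are illustrative, and Section 3.3 names only thrombocytopenia. The G-CSF part is a lesser matter of recovery parameters. The trial's primary endpoints are not affected by this point.

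**What to change.** 1. **Abstract the data.** Before the model is fitted, extract for the Phase I PK/PD patients (at most 21) the date and units of each platelet transfusion and the product, dose and dates of G-CSF. Cover at least Cycle 1, and any later cycle whose counts are modelled.
2. **Amend 8.3.** State that concomitant medications are not collected except for these items.
3. **Amend 14.2.** State that each transfusion enters the model as a platelet input, or that counts within a fixed window after it are excluded or censored. State that G-CSF enters as a time-varying effect on neutrophils.

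A new prospective eCRF page for Phase Ib is not needed for this purpose: those patients give no PK/PD samples, and the current text was written with Phase I results in hand.

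The cost is modest chart and blood-bank abstraction at Roswell Park, plus some modelling work. Appendix E carries Phase 1 registration instructions for network sites; if any Phase I patient was in fact treated at one, the abstraction would extend there. No visit, sample, patient or clinical rule changes.
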